Malignant pleural effusion (MPE) is common, and is estimated to affect up to a half of patients with malignancy, either at the time or during subsequent clinical course after the diagnosis of malignancy. Lung cancer is the most common cause of MPE, followed by breast cancer, lymphoma, unknown primary genitourinary and gastrointestinal carcinoma. Pleural involvement indicates dissemination of malignancy and suggests a poorer prognosis and the median survival rate ranges from 3 to 12 months, with lung cancer showing the shortest survival among Caucasian cohorts. Patients with MPE frequently suffer from effusion related symptoms requiring therapeutic drainage. Conventionally, the options of therapeutic drainage of MPE include needle aspiration, and intercostal drain insertion with or without chemical pleurodesis. Needle aspiration allows quick relief of effusion and symptoms, though the volume of pleural effusion being aspirated with each attempt of needle puncture is limited to 1-1.5 litres, and repeated puncture involves risks of complications. Intercostal drain insertion will allow gradual drainage of large pleural effusion over days, but the shortcomings being the long hospitalization of at least a week, and the presence of trapped lung would preclude chemical pleurodesis for definitive fluid control. Up to 40% of MPE patients still require repeated pleural drainage procedure, even after Talc chemical pleurodesis. The much longer hospitalization period is considered unfavourable for patients with limited lifespan in terms of weeks or a few months, who would spend more time with their family. In recent few years, indwelling pleural catheter (IPC) has provided a relatively novel option of palliative MPE drainage, on an ambulatory out-patient setting. IPC has been reported to be cost-effective, in particular for patients with survival of less than 14 weeks. With the limited time span, it is important to balance between the aim of symptomatic relief and maintaining patient's quality of life. Invasive procedures and prolonged hospitalisation can cause great distress to patients. Predicted survival of patients with MPE would be important in informing the most suitable method for relieving MPE. Previous studies have identified relevant factors on prediction of survival in patients with malignant pleural effusion but so far, there is no data for Chinese patients. The LENT scoring system (pleural fluid lactate dehydrogenase, Eastern Cooperative Oncology Group performance score, neutrophil -to-lymphocyte ratio and tumour type) is a new validated prognostic score in malignant pleural effusion.

This study aims to identify prognostic factors and evaluate the use of LENT score in Chinese patients with malignant pleural effusion that can subsequently shed light on the treatment approach.

Objectives

To investigate the prognostic factors predicting survivals and need of repeated pleural drainage in patients with malignant pleural effusion

Trial Design:

Longitudinal cohort study, observational

Study investigations:

Patients are retrospectively identified from Hospital Authority Clinical Management System. Clinical Data Analysis and Reporting System (CDARS) will be used to retrieve the list of adult subjects (age 18 or above) having been investigated at Queen Mary Hospital, with the diagnosis of malignant pleural effusion from 2010 and onwards. Upon commencement of the current study, patients newly diagnosed to have malignant pleural effusion, who are under the care of Department of Medicine, will also be prospectively recruited and informed consent will be obtained for use of their data. Their baseline demographic data, blood test results and pleural fluid results will be retrieved/ collected, and data on their subsequent clinical course will also be collected for study purpose. The blood tests and pleural fluid workups are all clinical routine investigations, and study only involves data utilization. The study does not involve any additional interventions for the subjects.

The study does not involve retrieval of sensitive data, nor any active interventions on study subjects. Data will be anonymous and the individuals will not be identifiable. Any database collected will be encrypted. Therefore, for retrospectively found subjects, irrespective of their status at the study time (alive or dead), informed consent will not be actively pursued.

The following data will be collected:

1. Baseline characteristics:

Patient variables including age, performance status and other co-morbidities will be collected at the start of study, and at the time of diagnosis of MPE.

2. Blood tests data:

Variables at initial diagnosis will be collected including complete blood count, inflammatory variable such as C-reactive protein, lactic dehydrogenase, protein and albumin levels.

3. Pleural fluid data:

Variables including pH, glucose, lactic dehydrogenase and protein level will be collected.

Outcomes:

1. Primary outcome/endpoints:

Rate of fluid recurrence requiring invasive pleural interventions

2. Secondary endpoints:

Survival

Need of definitive fluid control measure

Complications of pleural interventions

Statistical analysis

Multivariable Cox model and linear regression will be undertaken to identify factors predictive of survival and need of pleural tapping. A modified LENT score (pleural fluid lactate dehydrogenase, Eastern Cooperative Oncology Group performance score, neutrophil -to-lymphocyte ratio and tumour type) will be investigated for risk stratification using the Kaplan Meier survival curve and Receiver Operating Characteristic curve analysis.

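### Prospective patients must live to consent, and no time origin or delayed entry is set, so pooled Kaplan-Meier survival could be overstated early in follow-up

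*Combined protocol and SAP*

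**What the plan says.** Under Study investigations, two routes lead into one cohort. The first is a retrospective list of adults "having been investigated at Queen Mary Hospital, with the diagnosis of malignant pleural effusion from 2010 and onwards", with no end date given. For these patients, "irrespective of their status at the study time (alive or dead), informed consent will not be actively pursued". The second covers newly diagnosed patients under one department, who "will also be prospectively recruited and informed consent will be obtained for use of their data". The time from diagnosis to consent is not stated.

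Survival is a secondary endpoint with no start date. Patient variables are collected on two occasions, study start and MPE diagnosis, and blood variables at initial diagnosis. Neither occasion is named as time zero.

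Under Statistical analysis: "Multivariable Cox model and linear regression will be undertaken to identify factors predictive of survival and need of pleural tapping". The modified LENT score is to be examined for "risk stratification using the Kaplan Meier survival curve and Receiver Operating Characteristic curve analysis". Nothing is said about entry times, or about whether the two cohorts are pooled, stratified or analysed separately.

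**The concern.** A patient on the consent route cannot contribute a death before consent. If survival is nevertheless counted from diagnosis, the survivors' time before consent enters the curve as event-free time while the matching deaths are absent. This is left truncation, and plain Kaplan-Meier does not handle it. The error is upward and falls on the earliest part of the curve. If prospective time ran from consent instead, this calculation would not apply, but a pooled curve would mix two time origins.

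The early part of the curve matters here. The opening background text says that "Predicted survival of patients with MPE would be important in informing the most suitable method for relieving MPE", and reports one drainage option as "cost-effective, in particular for patients with survival of less than 14 weeks". A reader is therefore likely to look at absolute survival over the first few months.

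**Working it through.** The plan gives no survival estimate, sample size, consent lag or prospective share, so there is no figure of its own to reproduce.

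**Inputs from the plan.** "the median survival rate ranges from 3 to 12 months" (both ends are used); 14 weeks as a time point of interest.

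**Assumptions, not in the plan.** Constant hazard; fixed consent lag d of 1, 2 or 4 weeks; prospective share p of enrolled patients of 10%, 25% or 50%; no censoring; deaths before consent not recovered; N = 300 for scale.

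**Step 1: deaths missed.** S(t) = 0.5^(t/median), with d in months = weeks × 7/30.4375. The share of prospective patients who die before consent is 1 − S(d). At lags of 1, 2 and 4 weeks this is 5.2%, 10.1% and 19.1% for a 3-month median, and 1.3%, 2.6% and 5.2% for a 12-month median.

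**Step 2: the pooled curve without entry times.** For t ≥ d, the observed curve is (1 − p)·S(t) + p·S(t)/S(d). Example with median 3 months, 2-week lag and p = 0.25: S(d) = 0.899, so 0.75 × 0.500 + 0.25 × 0.500/0.899 = 0.514 against a true 0.500.

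Median 3 months, shares 10% / 25% / 50%:

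| Lag | 3-month survival (true 50.0%) | 14-week survival (true 47.5%) | 1-month mortality (true 20.6%) |
|---|---|---|---|
| 0 | 50.0 | 47.5 | 20.6 |
| 1 week | 50.3 / 50.7 / 51.4 | 47.8 / 48.2 / 48.8 | 20.2 / 19.5 / 18.5 |
| 2 weeks | 50.6 / 51.4 / 52.8 | 48.1 / 48.9 / 50.2 | 19.7 / 18.4 / 16.2 |
| 4 weeks | 51.2 / 53.0 / 55.9 | 48.7 / 50.3 / 53.1 | 18.8 / 15.9 / 11.2 |

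Median 12 months: 3-month survival (true 84.1%) is overstated by 0.3 to 2.3 points at shares of 25% to 50%, and by 0.1 to 0.5 at 10%. If the share is defined among all diagnosed rather than enrolled patients, the 50%, 4-week, 3-month-median case is +5.3 rather than +5.9 points.

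**Step 3: does delayed entry remove it?** In simulations of 400,000 patients per scenario over the same grid, Kaplan-Meier with entry at consent gave, for the 3-month median, 3-month survival of 49.9% to 50.1% and 1-month mortality of 20.5% to 20.7%. With a randomly varying lag (mean 4 weeks, 50% prospective, 200,000 patients), the curve without entry times gave 54.7% at 3 months and delayed entry 50.1%. Both checks take the lag as unrelated to prognosis.

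**Step 4: scale against sampling error.** At N = 300 the standard error of 50% survival is √(0.5 × 0.5/300) = 2.9 points, so the 3-month bias at a 2-week lag is below one standard error. For a 25% share and 2-week lag, total error at 1 month is √(2.2² + 2.2²) = 3.1 points without entry times, against 2.5 with delayed entry. At 3 months it is √(1.4² + 2.9²) = 3.2 against 2.9.

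**Step 5: relative measures.** In a simulation with a three-level score, a true hazard ratio of 2 per level and lags up to 4 weeks, the hazard ratio without entry times was 1.996 to 2.015 and the AUC moved by at most 0.006. This covers one score structure and was not confirmed by a second calculation, so it is indicative.

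**Step 6: primary endpoint.** The plan does not define the rate of recurrence. Suppose it is the proportion with recurrence before death, with recurrence hazard r and death hazard λ. Among patients alive at d it is 1 − [λ/(λ + r)]·e^(−r·d). Assuming r = λ, this is 1 − 0.5·S(d), against a true 50.0%. At 2 weeks it is 1 − 0.5 × 0.899 = 55.05%; the 5.05-point excess times a share of 25% to 50% gives +1.3 to +2.5 points. At 4 weeks the shift is +2.4 to +4.8. With an assumed r of 0.1 per month, the shifts run from +0.8 to +3.1. If the rate is events per person-time with a constant hazard, there is no shift.

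**The case against.** The strongest reply is that the bias needs four conditions and the plan states none of them; if any one fails, it disappears or changes form. In particular, the retrospective list has no end date and takes deceased patients without consent, so patients who die before being approached might enter that way. The text neither says so nor rules it out. This stands: what is shown is a structural risk, not an error already made.

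Second, the stated aim is prognostic factors, with Kaplan-Meier serving score-based stratification, and 14 weeks is a background remark rather than an analysis time. This stands in part. Hazard ratios and AUC look robust, but Kaplan-Meier curves by score still display absolute survival in each group. The figures above are for one homogeneous curve and do not give the size within score groups.

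Third, the prospective share may be small, since the retrospective list covers hospital patients from 2010 while prospective recruitment is confined to one department. At a 10% share and a 3-month median, the 3-month overstatement is only 0.3 to 1.2 points over lags of 1 to 4 weeks.

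A reader might infer that the survival results will be biased, or that the prognostic modelling is invalid. The documents support neither: the conditions are open, and relative measures barely move. A reader might equally infer that only survival is exposed. That is not established either, because the recurrence rate is undefined.

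**Conclusion.** The plan combines a route that requires survival to consent with one that does not, and sets no time origin or entry rule. If all four conditions hold, absolute Kaplan-Meier survival is overstated. The central illustration (3-month median, 2-week lag, 25% to 50% share) is +1.4 to +2.8 points at 3 months and −2.2 to −4.4 points for 1-month mortality. The largest case examined (4 weeks, 50%) is +5.9 and −9.4. Lag, share and N are assumptions, and the constant hazard is a simplification. The proportion with recurrence could shift as well, by an amount that depends on the recurrence hazard. Severity is minor.

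**What to change.** Set time zero at MPE diagnosis for all patients, state whether the cohorts are pooled, and then choose one of two routes:

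- Include every newly diagnosed patient who dies before consent through record retrieval, where the approvals allow, and count everyone from diagnosis without delayed entry.
- Otherwise, record the consent date and let prospective patients enter the Kaplan-Meier risk set at consent. Use the same entry times in the Cox model for consistency; the hazard ratios above give no other reason to.

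In either case, show Kaplan-Meier survival by recruitment mode as a sensitivity check, because delayed entry does not correct selection by ability or willingness to consent. Define the recurrence rate as a proportion or as events per person-time.

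The cost is a few sentences, one recorded date, a standard entry-time option in survival software and one extra display. The date needs to be captured during recruitment, since it may not be recoverable later. The statistical price of delayed entry is wider early intervals. At an assumed N of 300 and a 3-month median, the 1-month standard error is about 2.5 against 2.2 points (25% share, 2-week lag), and at worst 3.3 against 1.8 (50%, 4 weeks). At 3 months it is 2.9 against 2.9, at worst 3.2 against 2.9.

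### Does collecting performance status and comorbidity at study start as well as at effusion diagnosis bias the survival models and the LENT score?

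*Combined protocol and SAP*

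**What the plan says.** The design is an observational cohort with two streams. Retrospective patients are those "with the diagnosis of malignant pleural effusion from 2010 and onwards"; newly diagnosed patients are recruited prospectively once the study begins.

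The data list gives timing item by item:

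- **Baseline characteristics:** age, "performance status and other co-morbidities will be collected at the start of study, and at the time of diagnosis of MPE".
- **Blood tests:** "Variables at initial diagnosis will be collected including complete blood count". The text does not say which diagnosis is meant.
- **Pleural fluid:** "Variables including pH, glucose, lactic dehydrogenase and protein level will be collected". No date is given.

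The primary outcome is "Rate of fluid recurrence requiring invasive pleural interventions"; survival is secondary. The Statistical analysis section names a multivariable Cox model, linear regression, and a modified LENT score assessed by Kaplan-Meier and ROC methods. It states neither a time origin nor which of the two performance-status values is used.

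**The concern.** A prognostic model needs predictors known at time zero. For a patient diagnosed years before the study opened, a value recorded at study start comes after time zero and requires the patient to have lived that long. The protocol itself recognises that retrospective patients may have died, since "irrespective of their status at the study time (alive or dead), informed consent will not be actively pursued". A study-start performance status would therefore exist only in survivors, and in those survivors it could come after the fluid recurrence it is meant to predict. Put into a Cox model or the LENT score, it would bring survivor selection (immortal time) into the result.

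The blood-test wording adds to the worry. The introduction says effusion can appear "either at the time or during subsequent clinical course after the diagnosis of malignancy". If the blood-test date meant the cancer diagnosis, the neutrophil-to-lymphocyte ratio could predate the effusion, and the LENT components would come from different dates. The score would then not be one a clinician could calculate when the effusion is found, which is the use the study has in mind.

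**Working it through.** The plan gives no sample size, event count or power, so there is no figure of its own to reproduce. Two things can be checked: how often a study-start value could exist, and whether the plan leads an analyst to use it.

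**1. Share of retrospective patients alive at study start**

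Inputs:
- Median survival *m*, from the introduction: "the median survival rate ranges from 3 to 12 months". I take 3, 6 and 12 months.
- Look-back *T* from study start to the earliest diagnosis. Diagnoses run from 2010 but the start date is not given, so *T* is an assumption.
- Assumed: diagnoses spread evenly over *T*, and exponential survival with hazard *d* = ln 2 / *m*.

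Formula: share alive = (1 − e^(−dT)) / (dT).

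Example, *m* = 12 and *T* = 36 months: dT = 0.6931 × 3 = 2.079; e^(−2.079) = 0.125; share alive = 0.875 / 2.079 = 42.1%.

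| Look-back | m = 3 mo | m = 6 mo | m = 12 mo |
|---|---|---|---|
| 1 year | 33.8% | 54.1% | 72.1% |
| 2 years | 18.0% | 33.8% | 54.1% |
| 3 years | 12.0% | 23.7% | 42.1% |
| 5 years | 7.2% | 14.4% | 28.0% |
| 8 years | 4.5% | 9.0% | 18.0% |

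For look-backs of 3 to 8 years, the study-start value is unobtainable for 100 − 42.1 = 57.9% up to 100 − 4.5 = 95.5%. More than half are dead only once *T* exceeds about 0.6, 1.1 or 2.3 years for the three medians. At a 12-month median, a 1-year look-back gives 28% dead and a 2-year look-back 46%. A longer-tailed Weibull (shape 0.6 to 0.7) gives 54% to 55% dead at 3 years with a 12-month median. So the statement that most have died is plausible but depends on a date the documents do not give.

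**2. What misuse would cost**

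Take *T* = 60 and *m* = 6 months (*d* = 0.1155 per month) and no predictor effect at all.

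- Alive at study start: time from diagnosis is elapsed time plus residual life, close to a sum of two exponentials with survivor function e^(−dt)(1 + dt). This equals 0.5 at dt = 1.678, so the median is 1.678 / 0.1155 = 14.5 months.
- Already dead: density proportional to d·e^(−dt)(1 − t/60), median 5.1 months.

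The gap arises only from whether a study-start value could be recorded. The hazard is real if that value is modelled.

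**3. Does the plan lead there?**

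- The quoted sentence names effusion diagnosis as a collection time. That is the anchor any correction would ask for, and it is already planned.
- The Statistical analysis section never assigns the study-start value to a model or to the score.
- Part 1 shows the study-start value to be the less available one. The diagnosis value is the one that can be sought for living and dead patients alike.
- With two streams, the two dates have a natural reading: entry for prospective patients, where it should lie close to diagnosis, and effusion diagnosis for retrospective ones.
- In the study-investigations text and the data list, every other mention of a diagnosis is of the effusion, including the item just before the blood tests. The blood-test phrase most naturally means the same. The contrary reading rests on an epidemiological remark in the introduction.

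**The case for a change.** The strongest reply is that both values stand under a baseline heading, for all patients, and no sentence keeps the study-start value out of the models. The reading that separates the two streams is possible but not written. LENT combines performance status, neutrophil-to-lymphocyte ratio and pleural fluid LDH, and the plan gives these three different or unstated dates. The 14.5 versus 5.1 month contrast shows that misuse would be serious, and one sentence would rule it out at almost no cost.

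Part of this stands. The plan does omit the time origin and the rule for choosing a value, and a careful author would have written both. But the harm needs an analyst to pass over the planned diagnosis value for one that cannot be obtained in many of the retrospective patients. The contrast measures the effect of that error, not of the plan as written.

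The concern also reaches too far in two places. Performance status cannot be measured after death, so for survival the issue would be missing values and survivor selection; only for recurrence could the measurement follow the outcome. And for age, the two values differ only by elapsed calendar time.

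**Conclusion.** No change is called for. The value needed for valid prognostic modelling, performance status and comorbidity at effusion diagnosis, is already scheduled, and nothing directs the analyst to the other one. What is missing is a line of detail on time zero and predictor date, and the sensible default is clear: effusion diagnosis for every modelled predictor, with study-start values at most descriptive.

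The potential size is conditional. If study-start values were used, they would be missing for about 58% to 95% of retrospective patients, assuming look-backs of 3 to 8 years, even accrual, exponential survival and medians of 3 to 12 months; shorter look-backs lower this. The effect on the whole cohort cannot be stated, because the prospective share is not given. No bias in a hazard ratio, the score or the ROC analysis has been shown for the plan as written. The conclusion rests on reading the undated or loosely dated blood and pleural fluid items as referring to the effusion work-up, which the surrounding text supports.

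### Need of pleural tapping, most plausibly the primary endpoint, appears to be assigned to linear regression, with no rule for death before recurrence or unequal follow-up

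*Combined protocol and SAP*

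**What the plan says.** The regression plan is one sentence under Statistical analysis: "Multivariable Cox model and linear regression will be undertaken to identify factors predictive of survival and need of pleural tapping". It names two models and two outcomes and does not say which goes with which. The Objectives list the outcomes in the same order: "To investigate the prognostic factors predicting survivals and need of repeated pleural drainage in patients with malignant pleural effusion". The primary endpoint under Outcomes is "Rate of fluid recurrence requiring invasive pleural interventions", with no time window, denominator or unit. Survival is a secondary endpoint.

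Under Study investigations, the retrospective patients are those "with the diagnosis of malignant pleural effusion from 2010 and onwards", alive or dead at the time of the study. In addition, "patients newly diagnosed to have malignant pleural effusion, who are under the care of Department of Medicine, will also be prospectively recruited". Follow-up is described only as "data on their subsequent clinical course will also be collected for study purpose". No minimum follow-up, data cut-off date or censoring rule is given. The background says that "the median survival rate ranges from 3 to 12 months". Kaplan-Meier and ROC methods are mentioned only for risk stratification by a modified LENT score and are not assigned to recurrence.

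**The concern.** With median survival of 3 to 12 months, many patients will die before any recurrence. Because the cohort combines patients diagnosed since 2010 with new recruits, time under observation will also differ widely between patients.

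A linear model for ever/never tapping, or for a raw number of procedures, uses neither fact. Two things follow. A factor that shortens life leaves less time in which to need drainage, so it can appear to protect against recurrence. And patients seen for only a short time count as free of recurrence when they have not yet had time to recur.

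The study is meant to inform the treatment approach and wants both predicted survival and need of repeat drainage for that purpose. If the recurrence analysis carries survival within it, the two cannot be read separately.

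**Working it through.** The plan gives no sample size, event count or effect size, so there is no figure of its own to reproduce. The check asks how large the two effects could be.

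**Inputs.**
- Median survival of 9 versus 6 months: assumed, inside the 3 to 12 months in the background.
- Recurrence hazard r = 0.077 per month: assumed, chosen so that 40% ever recur at median survival 6 months. The 40% is borrowed from the background ("Up to 40% of MPE patients still require repeated pleural drainage procedure, even after Talc chemical pleurodesis") and is not a planning rate for this cohort. Range tried: 0.03 to 0.15.
- Constant hazards: assumed.

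**Formulas.** Death hazard d = ln 2 / median, so d = 0.0770 for 9 months and 0.1155 for 6 months. Share with recurrence observed by time t: P(t) = r/(r+d) × [1 − exp(−(r+d)t)]. With complete follow-up, P = r/(r+d), and the odds are r/d.

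**A factor that affects survival only (r = 0.077 in both groups).**

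| Follow-up | Median 9 months | Median 6 months | Difference (points) | Odds ratio |
|---|---|---|---|---|
| 3 months | 18.5% | 17.5% | 1 | 0.94 |
| 6 months | 30.2% | 27.4% | 3 | 0.87 |
| 12 months | 42.1% | 36.0% | 6 | 0.77 |
| Complete | 50.0% | 40.0% | 10 | 0.67 |

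The difference column is what a linear model on ever/never would estimate; the odds ratio is given for comparison. With complete follow-up the odds ratio is (r/0.1155)/(r/0.0770) = 0.67 whatever r is, and the gap is 7 to 10 points for r from 0.03 to 0.15.

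**A factor with hazard ratio 1.5 on both recurrence and death.** The odds ratio is 1.47, 1.39 and 1.21 at 3, 6 and 12 months. It reaches 1.0 only with complete follow-up.

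**Short follow-up.** At median survival 6 months, the 17.5%, 27.4% and 36.0% observed at 3, 6 and 12 months compare with an eventual 40.0%. For r = 0.05 the 3-month figure is 11.8% against 30.2%; for r = 0.10 it is 22.1% against 46.4%. If follow-up is uniform over 0 to 12 months, the average observed share is 24.4%. If 20% of the cohort is like that (assumed), the overall figure is 0.8 × 40.0 + 0.2 × 24.4 = 36.9%. If 40% is, it is 0.6 × 40.0 + 0.4 × 24.4 = 33.8%.

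**Hazard shape.** If recurrence can occur only in the first 1 or 3 months, again calibrated to 40% at median survival 6 months, the survival-only factor gives odds ratios of 0.97 and 0.92, or gaps of 0.7 and 2.0 points. The direction is unchanged; the size is much smaller.

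**If a per-patient rate (count divided by follow-up) is analysed instead.** In simulation (assumed 200 patients, recurrence hazard ratio 1.5, between-patient variation in recurrence), linear regression on the rate kept the false-positive rate near 5%. Power was 21 to 31%, against 39 to 47% for negative binomial regression with a follow-up offset.

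**The case against.** The pairing is inferred. Without the word respectively, the sentence also allows Cox for both outcomes. The step from tapping to invasive pleural interventions is a second inference, though the Objectives support it. Both points stand, so the text does not establish that linear regression is the chosen analysis of the primary endpoint.

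No scoring of tapping is stated either, and the word rate may mean events per person-time. On that reading the harm is lost efficiency. This also stands.

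Absolute need of drainage before death is a legitimate target, and the Objectives speak of need. With complete follow-up, the contrast in the table is then correct and not a bias. Unequal follow-up remains a problem for either target, but the calculation above shows only that it lowers the overall level. How far it distorts predictor effects depends on how follow-up varies with the predictors, about which the documents say nothing.

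Three stronger readings are tempting and not supported:
- That every factor's apparent effect on recurrence is divided by its effect on death, so that a factor raising both equally disappears. This needs constant hazards and complete follow-up, and it concerns odds or count ratios, whereas a linear model estimates differences.
- That the distortion from death and the loss from short follow-up reach full size together. The table shows that short follow-up shrinks the first.
- That Cox regression alone would settle the matter. Censoring at death gives the cause-specific hazard and leaves absolute need unaddressed.

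**Conclusion.** The point holds in conditional form. Linear regression, on the natural reading, is a poor stated method for the endpoint that matters most, and the documents supply no handling of death or follow-up that would rescue it. If tapping is scored ever/never or as a raw count, a moderate survival difference could produce an apparent recurrence difference of about 1 to 10 percentage points, depending on follow-up, at a constant hazard of 0.077 per month; it is smaller if recurrence comes early. Brief follow-up could lower observed recurrence from 40.0% to 17.5% among patients seen for 3 months, and to 33.8–36.9% overall under the assumed mixes. All sizes are illustrative. The direction follows from the design, given that scoring.

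A reader might infer that the plan has committed to a biased primary analysis. The text does not go that far, since neither the pairing nor the scoring is stated. It should be corrected before analysis; confidence is medium.

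**What to change.** Assign each model to its outcome in the Statistical analysis section:
- **Survival:** multivariable Cox regression, censored at last follow-up.
- **Primary endpoint:** in place of linear regression, time from a defined start (for example the first drainage for malignant effusion) to first recurrence requiring an invasive pleural intervention. Report cause-specific Cox hazard ratios, censored at death and last follow-up, for the tendency to recur. Report cumulative incidence with death as a competing event for absolute need of repeat drainage, with a Fine-Gray model if adjusted effects on that scale are wanted.
- **Number of procedures, if wanted:** negative binomial regression with log follow-up time as offset.

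State the data cut-off. Add to the data list the dates of the starting procedure, repeat procedures, death and last contact.

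The cost is a few sentences of analysis text, a little more data extraction and somewhat more analysis. The two recurrence measures may point in different directions, and the report will have to explain why.

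### Does modelling the need for pleural tapping leave the primary endpoint, recurrence requiring any invasive procedure, without an analysis?

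*Combined protocol and SAP*

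**What the plan says.** Three places describe the outcome that is not survival, each in different words.

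- **Objectives:** prognostic factors are sought for survival and for "need of repeated pleural drainage in patients with malignant pleural effusion".
- **Outcomes, primary endpoint:** "Rate of fluid recurrence requiring invasive pleural interventions". No type of procedure is singled out.
- **Statistical analysis:** a multivariable Cox model and linear regression are to "identify factors predictive of survival and need of pleural tapping".

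The only other analysis sentence concerns a modified LENT score, with Kaplan-Meier and ROC curves, and names no recurrence outcome. The secondary endpoints include "Need of definitive fluid control measure".

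The introductory background text treats the procedures as distinct: "Conventionally, the options of therapeutic drainage of MPE include needle aspiration, and intercostal drain insertion with or without chemical pleurodesis". It then adds that "indwelling pleural catheter (IPC) has provided a relatively novel option of palliative MPE drainage".

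**The concern.** A pleural tap, taken at face value, is a needle aspiration, which is only one of the options in the background text. If the model counts taps alone, a patient whose recurrence is treated by drain, pleurodesis or indwelling catheter has a primary-endpoint event that the regression does not see. The phrase also drops the idea of recurrence, which is in the endpoint, and of repetition, which is in the objective.

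Two things would be at stake. Two analysts could code the event differently in a partly retrospective cohort whose records already exist. And a factor that influences only which procedure is chosen, not whether fluid returns, could appear prognostic. That matters because the study hopes to inform how such patients are managed.

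**Working it through.** The documents give no figure on this point: no sample size, event count, length of follow-up or procedure mix. The check is therefore mainly a comparison of the texts.

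**1. Objective against analysis sentence.** Both name a pair of outcomes, in the same order and with the same construction: survival first, then the need for a pleural procedure. The objective's second item is "need of repeated pleural drainage in patients with malignant pleural effusion"; the analysis sentence puts tapping in that position. The simplest reading is that one restates the other.

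**2. What the narrow reading would imply.**
- The Outcomes list has four items: recurrence requiring intervention, survival, definitive fluid control, and complications. Needle taps alone are not among them, so the regression would address an outcome that the study never lists.
- The primary endpoint and the second half of the objective would both lack a named model.
- The background text calls the single procedure needle aspiration. It never uses tapping for it, so the documents do not establish tapping as a technical term for one technique.

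**3. Could the first diagnostic tap be counted?** The plan says of the fluid: "Variables including pH, glucose, lactic dehydrogenase and protein level will be collected". The Study investigations section lists these results with the baseline data and treats later clinical events separately. If the sampling tap counted, nearly every patient with a fluid result would be an event and there would be almost nothing to predict. No reasonable analyst would code it so.

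**4. Illustration of the narrow reading, on assumed values only.** Let R be the proportion with a recurrence needing any procedure (equal in two groups), s the share of those tapped at first recurrence, and t the share of the rest tapped later.

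- Proportion ever tapped = R × [s + (1 − s) × t]
- Share of endpoint patients not counted = (1 − s) × (1 − t)

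With R = 0.40 and s = 0.40 v 0.80:

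| t | Ever tapped | Risk ratio | Not counted |
|---|---|---|---|
| 0 | 0.40 × 0.40 = 0.16 v 0.40 × 0.80 = 0.32 | 0.50 | 0.60 v 0.20 |
| 0.25 | 0.40 × 0.55 = 0.22 v 0.40 × 0.85 = 0.34 | 0.65 | 0.45 v 0.15 |
| 0.50 | 0.40 × 0.70 = 0.28 v 0.40 × 0.90 = 0.36 | 0.78 | 0.30 v 0.10 |
| 1 | 0.40 v 0.40 | 1.00 | 0 v 0 |

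Reversing the shares gives 2.00, 1.55, 1.29 and 1.00. A milder split, 0.50 v 0.80, gives 0.625, 0.735, 0.833 and 1.00. Equal shares give 1.00 throughout, with events lost but the ratio undistorted. R cancels from the ratio.

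The one related figure in the documents, "Up to 40% of MPE patients still require repeated pleural drainage procedure, even after Talc chemical pleurodesis", is an upper bound after one treatment. It is not a recurrence rate for this cohort and tells us nothing about s or t. The table also compares simple proportions, whereas the plan is for Cox and linear regression.

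**The case for a change.** The best case for a change is that the authors had a generic term available and did not use it. The background text speaks of repeated drainage procedures and the objective uses nearly the same words, yet the analysis sentence chooses another. Because definitive fluid control is a separate secondary endpoint, an analyst might take tapping to mean the non-definitive remainder. Nothing in the documents states otherwise, and aligning the words would be cheap.

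Part of this stands. The term is undefined, three wordings are in use, and borrowing the endpoint's phrase would read better.

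The inference to a narrower outcome does not stand. The analysis section says nothing about definitive fluid control, so it draws no contrast from which a remainder could be deduced. The fuller remedies (a list of qualifying procedures, rules for staged procedures and for drainage through a catheter already in place, and whether one procedure can count for two endpoints) are matters of how the primary endpoint is defined. The analysis wording did not create them, and swapping one phrase would not settle them. Nor would it say which model belongs to which outcome, which is a separate question.

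**Conclusion.** The inconsistency is real, but it is one of terminology. Tapping most naturally restates the objective's repeat drainage and so points to the primary endpoint; on that reading the effect on results is nil. An analyst working from the Outcomes list would code recurrence requiring any invasive pleural procedure, because that is the only such outcome listed as primary. The narrow reading requires an outcome that the study does not list, and would leave the declared primary endpoint without a model.

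If the authors did mean needle taps only, the distortion could run in either direction or be absent. Its size cannot be derived from the documents, since R, s and t are all assumed. The conclusion rests on the parallel between the Objectives and the analysis sentence, not on an explicit definition. This is a gap in detail that analysts fill sensibly, and no change to the plan is called for.
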